### 3. OVERALL STUDY DESIGN

#### 3.1. Study Design

This is a Phase 2, multicenter, multinational, double-blind, randomized, placebo-controlled study evaluating the efficacy, safety, [REDACTED] quality of life [REDACTED] of two oral (PO) treatment doses of CC-90001 (200 mg and 400 mg QD), compared with placebo, for an initial 24 weeks of treatment, in subjects with IPF. This study will also assess the efficacy and long-term safety in the 80-week Active Treatment Extension Phase when all IPF subjects will receive CC-90001 (200 mg or 400 mg PO QD). This study is designed to assess response to treatment by using measures of lung function, disease progression, fibrosis on radiography, and patient-reported outcomes, including cough, dyspnea, and quality of life assessments. It will also assess dose response.

Approximately 165 adult male and female subjects with a diagnosis of IPF (Lynch, 2018) will be randomized 1:1:1 (55 subjects per arm) to treatment with CC-90001 (200 mg or 400 mg PO QD) or matching placebo for an initial 24 weeks. Subjects receiving concurrent protocol-allowable standard of care (SOC) therapy are eligible to participate in the study. Approximately 75 subjects (25 subjects per arm) receiving protocol-allowable SOC are to be enrolled in the study. The randomization will be stratified based on the concurrent administration of protocol-allowable SOC (Yes/No). Subjects not receiving concurrent protocol-allowable SOC therapy will also be stratified by previous exposure to either pirfenidone or nintedanib (Yes/No).

[REDACTED] Subjects completing 24 weeks of treatment will continue onto the 80-week Active Treatment Extension Phase. Subjects who enter and complete the 80-week Active Treatment Extension Phase will receive treatment for a total of 104 weeks (Figure 1).

Following an initial screening at Visit 1, eligible IPF subjects will be randomized to receive either CC-90001 200 mg or 400 mg PO QD or matching placebo beginning on Day 1 (Baseline [Visit 2]) of the study. At Week 24, all subjects originally randomized to receive placebo will be re-randomized 1:1 to blinded CC-90001 (200 mg or 400 mg PO QD) via interactive web response system (IWRS). All IPF subjects originally randomized to CC-90001 (200 mg or 400 mg PO QD) will remain on that same blinded treatment assignment during the 80-week Active Treatment Extension Phase. During the 80-week Active Treatment Extension Phase, all subjects not on concurrent protocol-allowable SOC therapy will have the opportunity, if deemed appropriate by the Investigator, to receive allowed SOC [REDACTED].

An interim analysis will be conducted when approximately 50 non-SOC IPF subjects have completed 24 weeks of treatment. If the safety and efficacy of CC-90001 are favorable, a separate [REDACTED] substudy in subjects with progressive pulmonary fibrosis (PPF) will be initiated (refer to Section 3.1.1).

A second interim analysis is planned after approximately 40 SOC IPF subjects have completed 24 weeks of treatment. The purpose of the additional interim analysis is to evaluate safety, tolerability and efficacy of CC-90001 in SOC IPF subjects, along with all study subjects enrolled into the study, and to determine if any treatment group should be discontinued.

All subjects who complete the study treatment phases and those subjects who discontinue investigational product (IP) prior to the completion of the study will participate in the 4-week Post-treatment Observational Follow-up Phase.

To ensure the safety of all subjects in the study, the external Data Monitoring Committee (DMC) and SMT will review safety data as described in the DMC charter and SMT plan. Close monitoring of safety data for all subjects will be conducted throughout the study and will include, but not be limited to, labs, ECGs, pulmonary function testing, and adverse events.

The blind should be maintained for persons responsible for the ongoing conduct of the study from first subject enrolled through last subject/last visit of the 4-week Post-Treatment Follow-up Phase of the study. Blinded persons may include but are not limited to: Clinical Research Physician, Clinical Research Scientist, Clinical Trial Manager, Study Statistician, Data Manager, Programmers, Clinical Research Associates.

The study will be conducted in compliance with the International Council for Harmonisation (ICH) of Technical Requirements for Registration of Pharmaceuticals for Human Use/Good Clinical Practice (GCP) and applicable regulatory requirements.

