g Spirometry, DLCO, and pulse oximetry will be assessed as part of the safety assessments for those subjects who discontinue for progressive disease during the 24-Week Double-blind Placebo-controlled and 80-Week Active Treatment Extension Phases.

- i Blinded IP will be packaged in 32 tablet-count, 16-day blister cards (16-day card includes IP for two additional days in the event the subject is unable to return for their scheduled visit).
  - On Visits 2 and 3, one blister card will be dispensed to the subject. Remaining IP from the blister card issued on Visit 2 will be reissued to the subject along with a new card on Visit 3. The subject should be instructed to finish the remaining IP in the blister card issued at Visit 2 before starting the new blister card issued at Visit 3.
  - On Visits 4 to 8, two blister cards will be dispensed to the subject per visit.
  - On Visits 9 and 10E, one blister card will be dispensed to the subject. Remaining IP from the blister card issued on Visit 9 will be reissued to the subject along with a new card on Visit 10E. The subject should be instructed to finish the remaining IP in the blister card issued at Visit 9 before starting the new blister card issued at Visit 10E.
  - On Visits 11E to 16E, two blister cards will be dispensed to the subject per visit.
  - On Visit 17E to 24E, three blister cards will be dispensed to the subject per visit.
  - On Visit 25E, two blister cards will be dispensed to the subject per visit.
- j Final dose of IP administered at the investigative site.
- k For all subsequent visits, an administrative window of  $\pm 3$  days is permitted. Scheduling of Visits 3 to 9 is based on Visit 2 (randomization date) and scheduling of Visits 10E to 26E is based on Visit 9 (re-randomization date). The Post-treatment Observational Follow-up Visit is scheduled 28 days (4 weeks) after the date of the last dose of IP  $\pm 3$  days.
- l If a subject has adequate documentation of successful treatment for either latent or active TB, the QuantiFERON-TB Gold test is not needed. Instead, a chest radiograph, obtained within the 12 weeks prior to Screening or during Screening, without changes suggestive of active TB infection as determined by a qualified radiologist, will be sufficient to permit further participation in the study for these subjects. Documentation of adequate treatment for TB must be obtained prior to randomization.

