## 6.2. Treatment Phase

The subject will begin treatment upon confirmation of eligibility at the Baseline (Visit 2). For all subsequent visits, an administrative window of  $\pm 3$  days is permitted. Scheduling of Visits 3 to 9 is based on Visit 2 (randomization date) and scheduling of Visits 10E to 26E is based on Visit 9 (re-randomization date).

The following evaluations will be performed at the frequency specified in the Table of Events, [Table 5](#) and in the order described below. The evaluations should be performed prior to dosing on the visit day, unless otherwise specified.

- Adverse event evaluation
- Concomitant medications reviewed with the subject
- Concomitant procedures reviewed with the subject
- Patient-reported outcome questionnaires will be completed as described in [Section 6.7](#)
- Assessment for new or worsening shortness of breath

As part of the routine assessments during the study visit, subjects will be assessed for new or worsening of shortness of breath (SOB). The Investigator should use his/her clinical judgement to decide how to further assess and treat such subjects.

Subjects who experience and receive adequate treatment for SOB with permitted drugs (see [Section 8.1.2](#)) but demonstrate further clinical decline and/or decrease of  $\geq 10\%$  from baseline in % predicted FVC at two consecutive evaluations at a minimum of 4 weeks between evaluations should discontinue IP and enter the 4-week Post-treatment Observational Follow-up Phase (Table of Events, [Table 5](#)). Whether to discontinue a subject from study treatment who experiences unexplained worsening in hypoxemia (an absolute decrease from baseline of 4% or more in SpO2) will be left up to the Investigator's discretion. Treatment of subjects during the Post-treatment Observational Follow-up Phase is at the discretion of the Investigator.

All relevant clinical data (summary on clinical course, signs and symptoms; laboratory, lung function and imaging results; and treatment provided) relating to new or worsening shortness of breath must be collected by the Investigator. Changes in respiratory status that are considered by the Investigator as possibly or likely due to [REDACTED] disease progression will be reviewed further by the independent Adjudication Committee. Details regarding the adjudication process will be described in a separate charter.

- Efficacy assessments as described in [Section 6.4](#)

- 

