### 6.2.1. End of Treatment

An end of treatment (EOT) evaluation will be performed for subjects who are withdrawn from treatment for any reason as soon as possible after the decision to permanently discontinue treatment has been made.

The following evaluations will be performed as specified in the Table of Events, Table 5 and in the order described below:

- Adverse event evaluation
- Review of concomitant medications

- Review of concomitant procedures
- Patient-reported outcome questionnaires will be completed as described in Section 6.7
- Assessment for new or worsening SOB
- Efficacy assessments as described in Section 6.4

- 12-lead ECG as described in Section 6.1
- Complete physical examination (source documented only) in Section 6.1
- Vital signs as described in Section 6.2. All abnormal (out of range) value that constitutes an adverse finding (event), should be reported as an AE if appropriate
- Weight (to be done in street clothes, no shoes) will also be measured and recorded
- Clinical laboratory safety tests as described in Section 6.1, with the exception of those labs performed only at Screening (eg, QuantiFERON-TB Gold, hepatitis test, and postmenopausal testing)
- Counseling about pregnancy precautions and the potential risks of fetal exposure must be conducted.

- Study IP returned (all used and unused blister cards) and IP compliance will be assessed

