### 6.3. Post-treatment Observational Follow-up Phase

All subjects will be followed for 28 days after the last dose of IP for AE reporting, as well as SAEs made known to the Investigator at any time thereafter that are suspected of being related to IP, as described in Section 10.1. The Post-treatment Observational Follow-up Visit is scheduled 28 days (4 weeks) after the date of the last dose of IP  $\pm$  3 days.

The following evaluations will be performed as specified in the Table of Events, Table 5 and in the order described below:

- Adverse event evaluation (monitored through 28 days after the last dose of IP or until the last study visit, whichever is longer).
- Concomitant medications reviewed with the subject
- Concomitant procedures reviewed with the subject
- Assessment for new or worsening SOB
- Pulmonary function tests (for safety only):

- Spirometry (FEV1, FVC)
- DLCO
- Pulse oximetry
- 6MWT
- 12-lead ECG as described in Section 6.1
- Complete physical examination (source documented only). Refer to Section 6.1
- Vital signs including weight
- Clinical laboratory safety tests as described in Section 6.1, with the exception of those labs only performed only at Screening (eg, QuantiFERON-TB Gold, hepatitis test, and postmenopausal testing)
- Counseling about pregnancy precautions and the potential risks of fetal exposure must be conducted

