## 9. STATISTICAL CONSIDERATIONS

### 9.1. Overview

This is a double-blind, randomized, placebo-controlled study with two treatment arms of oral CC-90001 (200 mg or 400 mg PO QD), or one treatment arm in the PPF substudy, compared to placebo. This study consists of a 24-week Double-blind Placebo-controlled Treatment Phase, an 80-week Active Treatment Extension Phase, and a 4-week Post-treatment Observational Follow-up Phase. The primary efficacy analysis of percentage point difference in the percent predicted FVC at Week 24 and the secondary analyses will be performed after all IPF subjects complete the 24-week Double-blind Placebo-controlled Treatment Phase (Weeks 0 to 24) or terminate early prior to the Week 24 visit, and similarly but separately for the PPF subjects. Additional analyses will also be performed after the final database lock when all subjects complete the study or terminate early. This section outlines the statistical analysis strategy and details will be documented in a separate Statistical Analysis Plan (SAP) prior to unblinding of the treatment assignments for the 24-week Double-blind Placebo-controlled Treatment Phase of the study. The randomization schedule will be generated and implemented by the IWRS vendor.

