### 9.2. Study Population Definitions

The safety population will include all randomized subjects who received at least one dose of IP. The analysis of safety data in this study will be based on the safety population and subjects will be included in the treatment group they actually received.

The Full Analysis Set (FAS) will include all randomized subjects who received at least one dose of IP. The analysis of efficacy data in this study will be primarily based on the FAS and subjects will be included in the treatment group to which they are randomized.

The Per Protocol (PP) population will include all randomized subjects who received at least one dose of IP, have Baseline (Visit 2) and at least one post-Baseline FVC evaluation, and have no important protocol deviation during the 24-week Double-blind Placebo-controlled Treatment Phase. The final determination of important protocol deviation criteria will be made prior to the unblinding of the database and will be separately documented.

The FAS and PP populations will be analyzed separately for the IPF study and the PPF substudy.

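### Subjects who stop IP before about Week 20 have no scheduled Week 24 FVC or vital-status check, so the Week 24 effect regardless of stopping can only be modelled.

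*Combined protocol and SAP*

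**What the plan says.** **After stopping IP.** Section 3.1 sends early stoppers to the short follow-up phase: "those subjects who discontinue investigational product (IP) prior to the completion of the study will participate in the 4-week Post-treatment Observational Follow-up Phase". Two visits result. Section 6.2.1 gives the first: "An end of treatment (EOT) evaluation will be performed for subjects who are withdrawn from treatment for any reason", held promptly once the decision is made. Footnote k of Table 5 gives the second: the "Post-treatment Observational Follow-up Visit is scheduled 28 days (4 weeks) after the date of the last dose of IP", within three days either way. Table 5 has spirometry at both, and Section 6.3 introduces the follow-up measurements with the words "Pulmonary function tests (for safety only". No later column of Table 5 applies to these subjects. Section 11.2 asks for liver enzymes to be followed to resolution after a transaminase stop, but this is not an FVC or a dated vital-status check.

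**The analysis.** Table 2 places the primary endpoint, percent predicted FVC, at Week 24. For efficacy, Section 9.2 says that "subjects will be included in the treatment group to which they are randomized"; the analysis set requires at least one dose. Section 9.6.1 fits an MMRM to post-baseline values up to Week 24. It adds a Rank-ANCOVA in which deaths take the worst rank and other stops are imputed by a scheme left to the SAP.

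**Stops that the protocol directs.** Section 9.7.2 requires one after a confirmed absolute fall of 10 points in percent predicted FVC. Section 11.2 directs one after a confirmed transaminase elevation.

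**Late events.** Under Sections 10.1 and 10.5, routine recording ends 28 days after the last dose, or for SAEs at the last study visit if that is later. After that, only SAEs suspected to be IP-related are reported. Section 10.2.6 separately requires SAEs unresolved at exit to be followed.

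**The concern.** The endpoint is tied to a calendar week, but follow-up after stopping is tied to the last dose. For an early stopper the two do not meet. Those affected are not a random subset: one mandatory stop is triggered by the primary measure itself, and another by a laboratory finding whose frequency could differ by arm.

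Two things are at stake. First, without Week 24 values from stoppers, the trial cannot observe the effect at Week 24 in all treated randomized subjects whether or not they stayed on IP. Second, the worst-rank analysis needs to know who had died by Week 24. A death after the 28-day visit that is not suspected to be IP-related, and does not follow from an SAE unresolved at exit, may never be recorded. The subject would then be handled as a non-death stop. Neither FVC nor vital status that was not collected can be relied on to be recovered later.

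**Working it through.** **1. When follow-up reaches Week 24.** Inputs: Week 24 = day 168 ± 3, counting baseline as Week 0 (Table 5); follow-up = last dose + 28 ± 3 days (Table 5, footnote k).
- Earliest last dose whose follow-up can reach the window: 168 − 3 − 31 = day 134 (Week 19.1).
- Latest last dose whose follow-up can still fall in the window: 168 + 3 − 25 = day 146 (Week 20.9).
- Gap between the last scheduled FVC and Week 24 for a stop at week w: 24 − (w + 4). Stops at Weeks 8, 12 and 16 give gaps of 12, 8 and 4 weeks.

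The example in Section 9.7.2 (fall confirmed at Visits 4 and 5, that is Weeks 4 and 8) is an early case: a stop at Week 8 and a last FVC near Week 12. Stops at about Weeks 21 to 23 have FVC on both sides of Week 24, so little is lost there.

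**2. The yardstick.** Section 9.3 assumes differences of 3 (non-SOC) and 1.3 (SOC) with 45% on SOC: 0.55 × 3 + 0.45 × 1.3 = 2.235, which rounds to the stated 2.2.

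**3. Possible shift in the treatment difference.** Let f be the proportion of an arm without a Week 24 value, and d the mean gap between their true values and the model's projection. Each arm mean is off by f × d, so the between-arm shift is f1 × d1 − f2 × d2. The documents give neither f nor d; both are assumptions.

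| Missing, arm 1 v arm 2 | Projection error (points) | Between-arm shift | Share of 2.2 |
|---|---|---|---|
| Equal | Equal | 0 | 0% |
| 20% v 10% | 1 in both | 0.20 − 0.10 = 0.1 | 5% |
| 20% v 10% | 2 in both | 0.40 − 0.20 = 0.2 | 9% |
| 20% v 10% | 3 in both | 0.60 − 0.30 = 0.3 | 14% |
| 20% in one arm | 3 in that arm, no net error in the other | 0.60 − 0 = 0.6 | 27% |

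**4. One misclassified death.** In a 55 v 55 rank comparison the standard error of the rank sum is √(55 × 55 × 111 / 12) = 167.3. Moving one subject from the worst rank to percentile p passes about 55p subjects of the other arm, so z moves by about 55p / 167.3:
- 10th percentile: 5.5 / 167.3 = 0.03
- 25th percentile: 13.75 / 167.3 = 0.08
- median: 27.5 / 167.3 = 0.16

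This ignores covariate adjustment. The percentile is a range because the non-death imputation scheme is not in the supplied text.

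**The case against.** The best defence is that the plan is coherent for an effect while treated. The primary objective speaks of 24 weeks of treatment, the MMRM imputes nothing, and follow-up runs from the last dose. For FVC-triggered stops the fall is recorded at two evaluations before the stop, which is the kind of missingness MMRM handles well. This stands, and it rules out several stronger readings that a reader might infer:

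- *The primary analysis is biased.* The documents do not show this. The shift can be zero, and its size depends on quantities they do not give.
- *Section 9.2 commits the trial to a treatment-policy target.* It assigns subjects to arms and does not name an estimand.
- *Section 9.1 shuts out later values.* It runs the primary analysis once subjects finish the phase "or terminate early prior to the Week 24 visit". That sets timing only.
- *Follow-up FVC is excluded because of its safety label.* Section 9.6.1, read literally, takes all post-baseline values up to Week 24, and the SAP may settle the matter.

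The death issue is also narrow. It touches mainly a sensitivity analysis, and the on-treatment time-to-death summary in Section 9.6.2.1 is unaffected. P-values and intervals are declared descriptive.

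The defence does not fill the schedule gap. Redaction does not explain it, because the spirometry row and the early-termination and follow-up columns of Table 5 are legible. A SAP can choose an imputation rule, but it cannot supply a visit the protocol lacks.

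**Conclusion.** The point holds as a limit on what the trial can observe and as a cheap improvement worth making. With a last dose before about day 134, no Week 24 FVC or vital status is scheduled; that follows directly from the visit schedule.

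The consequence for the estimate is uncertain and may be nil. The 0.1 to 0.3 point range rests on assumed missingness of 20% v 10% with the same 1 to 3 point error in both arms. The 0.6 point figure needs 20% missing and a 3-point error in one arm with no net error in the other, so it should not be read as an expected size. The effect per misclassified death is small, and the documents give no basis for estimating how many there would be.

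**What to change.** 1. Ask subjects who stop IP before Week 24 to return for Week 24 spirometry, and check vital status at Week 24, unless consent is withdrawn.
2. Use those FVC values in a supplementary treatment-policy analysis beside the planned MMRM, and use the vital status in the worst-rank analysis.
3. Reconcile Section 9.7.2 with itself. Its rule takes the confirmed progressor off IP, while its example takes the subject out of the study. Section 11.1 lists progression as a reason to stop IP; Section 11.3 does not name it as a reason to leave the study. The answer decides whether progressors are still available at Week 24.

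**Cost.** One visit or contact per early stopper and one added analysis, with no extra patients. It needs an amendment with ethics approval (Section 13.5) and a revised consent form with re-consent of current participants (Section 13.3). The Week 24 values will also mix in other therapy, since Section 6.2 says: "Treatment of subjects during the Post-treatment Observational Follow-up Phase is at the discretion of the Investigator". For that reason the new analysis should supplement the MMRM and not replace it.

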### 3.1.1. Progressive Pulmonary Fibrosis Substudy

The exploratory substudy is a Phase 2, multicenter, multinational, double-blind, randomized, placebo-controlled study evaluating the efficacy, safety, [REDACTED] of one PO treatment dose regimen of CC-90001 (400 mg QD, unless review of benefit-risk favors 200 mg PO QD), compared with placebo, for an initial 24 weeks of treatment, in subjects with PPF. This substudy will also assess the efficacy and long-term safety in the 80-week Active Treatment Extension Phase when all PPF subjects will receive CC-90001. [REDACTED]

[REDACTED] This PPF substudy allows non-SOC subjects who were screened and did not receive a confirmed IPF diagnosis following central reading of HRCT and lung biopsy, if obtained, to be considered for the substudy. Enrollment into this substudy will not begin until after the first interim analysis and confirmation is received from the DMC that the overall main study in IPF subjects should continue as planned (Section 9.8).

Approximately 45 non-SOC subjects qualifying for enrollment into the substudy will be randomized in a 2:1 ratio (approximately 30 subjects in the CC-90001 arm and approximately 15 subjects in the placebo arm), for an initial 24 weeks. Subjects who enter and complete the 80-week Active Treatment Extension Phase will receive treatment for a total of 104 weeks. Refer to [Figure 2](#) for the PPF substudy design and [Section 4.2.2](#) for specific inclusion criteria.

[figure not shown]
Following an initial screening at Visit 1, eligible PPF subjects will be randomized to receive either CC-90001 or matching placebo beginning on Day 1 (Baseline [Visit 2]) of the study. At Week 24, all subjects originally randomized to receive placebo will receive CC-90001. All subjects originally randomized to CC-90001 will remain on that same blinded treatment assignment during the 80-week Active Treatment Extension Phase. The decision to receive additional treatments for pulmonary fibrosis [REDACTED] during the 80-week Active Treatment Extension Phase is at the discretion of the Investigator.

